7. NOTATION OF TREATMENT GROUPS AND VISITS

Notation of treatment groups

The following notation of **treatment groups** will be used throughout the report:

Full Notation (as used in the study protocol)	Notation Used Throughout All Tables, Listings, and Figures
Tapinarof Cream 1%	Tapinarof Cream 1%

Visit terminology

Visit	Notation Used Throughout All Tables, Listings, and Figures
Screening, Days -30 through Day -1, Visit V1	Screening
Baseline, Day 1, Visit V2	Baseline
Week 1, Day 8, Visit V3	Week 1
Week 4, Day 28, Visit V4 (End of Treatment)	Week 4
Week 5, Day 35, Visit V5 (End of Study/Follow-up)	Week 5

Note: A phone call to assess AEs and concomitant medications, to review study drug application procedures, and to confirm subject's continued participation in the study will occur on Week 2 (Day 15).

Analysis visits

Study days are measured from date of first dose of study medication. Study days corresponding to measurements are calculated as:

- Assessment date – date of first dose + 1 if assessment date is on or after the date of first exposure of treatment.
- Assessment date – date of first dose if assessment date is before the date of first exposure of treatment.

All efficacy, PK, and safety endpoints will be analyzed according to the nominal visits (i.e., actual visit) except for assessments collected on early termination and unscheduled visits. Early termination and unscheduled visits will be re-numbered to an analysis visit based on their windowed visits defined by actual study day. If more than one visit occurs within a single visit window, then the analysis will take the one closest to the target day. If the 2 visits are equidistant from the target day, the visit with later date and time will be used.

The following analysis visit windows will apply to early termination and unscheduled visits:

Analysis Visit	Target Day	Analysis Visit Window
Baseline	1	1
Week 1	8	Post first dose to Day 18
Week 4 (End of Treatment)	28	Day 19 – Maximum (last day of treatment + 3 days, Day 31)

Analysis Visit	Target Day	Analysis Visit Window
Week 5 (End of Study)	35	>Maximum (last day of treatment + 3 days, Day 31)

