6.3.4 Clinical Safety Laboratory Assessments

All protocol-required laboratory assessments must be conducted in accordance with the Study Reference Manual or Laboratory Manual and the protocol Schedule of Assessments ([Table 1](#)). Laboratory requisition forms must be completed, and samples must be clearly labeled with the subject number, protocol number, site number, and visit date. Details for the preparation and shipment of samples will be provided by the laboratory and are detailed in the Study Reference Manual or the Laboratory Manual. Reference ranges for all safety parameters will be provided to the site by the laboratory responsible for the assessments.

A list of clinical laboratory tests and parameters is provided in [Table 4](#).

All laboratory tests with values that are considered clinically significantly abnormal during participation in the study should be repeated until the values return to normal or baseline. If such values do not return to normal within a period judged reasonable by the Investigator, the etiology should be identified, if possible, and the Sponsor and Medical Monitor notified.

Table 4: Laboratory Tests

Diagnostic Screening Tests		

 • HBsAg • Hepatitis C antibody • Anti-HBc • Anti-HBs^a 		
 • Pregnancy tests: (serum at Screening and urine at other visits when performed; women of CBP only)^b • At the Investigator's discretion, subjects may be screened for alcohol and illicit drug use.
Serum Chemistry		

 • BUN • Creatinine • Glucose (fasting not required) • Sodium • Potassium • Chloride 	
 • Total carbon dioxide • Calcium • AST • ALT • Alkaline phosphatase 	
 • Uric acid • Total bilirubin (+fractionated if required) • Total protein • Albumin
Hematology		

 • Platelet count • RBC count • WBC count (absolute) • Reticulocyte count • Hemoglobin • Hematocrit 	
 • RBC Indices: • MCV • MCH • MCHC • Reticulocyte percentage 	
 • WBC Differential: • Neutrophils • Lymphocytes • Monocytes • Eosinophils • Basophils
Urinalysis		

 • Specific gravity • Microscopic examination (if blood or protein is abnormal) 		
 • Dipstick: pH, Glucose, Protein, Blood Ketones

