13.4 Clinical Laboratory Evaluation

Laboratory values will be classified as normal, low, or high based on normal ranges supplied by the laboratory. Changes from baseline in abnormality status will be summarized using shift tables.

For quantitative laboratory measures (chemistry and hematology), observed values and changes from baseline will be summarized descriptively by visit.

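### SAP Section 7 lets an unscheduled repeat displace an abnormal Week 4 laboratory value when the visit falls on Day 26 or 27, and SAP 13.4 has no worst-value table to offset it

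*SAP*

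**What the plan says.** SAP Section 7 analyses endpoints "according to the nominal visits (i.e., actual visit) except for assessments collected on early termination and unscheduled visits". Those two kinds of visit are renumbered by actual study day:

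- Week 1: target Day 8, window "Post first dose to Day 18".
- Week 4: target Day 28, window from Day 19 to the later of Day 31 and three days after the last day of treatment.
- Week 5: anything after that.

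The section then says: "If more than one visit occurs within a single visit window, then the analysis will take the one closest to the target day". If two are equally near, "the visit with later date and time will be used". The section does not say that a scheduled visit outranks an unscheduled one. Nor does it say whether selection is made for whole visits or separately for each parameter.

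Protocol 6.3.4 says that laboratory values judged clinically significantly abnormal "should be repeated until the values return to normal or baseline". Protocol 7.8 provides unscheduled visits at which blood may be drawn.

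SAP 13.4 says: "Changes from baseline in abnormality status will be summarized using shift tables". It adds by-visit descriptions of observed values and changes for chemistry and hematology. It has no shift to the worst post-baseline value.

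**The concern.** Change from baseline in laboratory values is a primary endpoint. A child who completes treatment has one routine post-baseline draw, at Week 4; the Day 35 draw is taken only if needed. A repeat soon after Week 4 is not a random second measurement: it is taken because the first value was abnormal. A rule that can choose the repeat purely because its date is nearer Day 28 therefore makes an error with a direction. The shift table could show a child as normal whose scheduled value was clinically significantly abnormal.

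The same rule has two further effects. An unscheduled value obtained shortly before Week 4, for example during follow-up of an adverse event, usually loses to the scheduled visit. An early-termination assessment up to Day 18 usually loses to a completed Week 1 visit, so the last status of a child who stopped early is missing from the by-visit tables.

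**Working it through.** The plan gives no figure to reproduce: the study is descriptive, with no hypothesis or power calculation. The check applies the Section 7 rule to every permitted combination of days. Results count day pairs and are not probabilities.

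**Inputs.** Week 4 visit on Days 26-30 (Protocol 7.5, Day 28 ±2). Week 1 visit on Days 7-9 (Protocol Table 1, ±1) or Days 6-10 (Protocol 7.3, ±2); these two need reconciling, and both were run. Windows and tie rule from SAP Section 7. The last dose is assumed to be the day before the Week 4 visit, following the intended-dose definition in Protocol 3.3. Cohorts of about 12, minimum 10 (SAP Section 5).

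**1. Repeat on a later day than Week 4.** With visit day d and repeat day r > d, the repeat is chosen if |r − 28| ≤ |d − 28|; equality counts because the later visit wins ties. The window ends on Day max(d − 1 + 3, 31).

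| Week 4 day | Possible repeat days | Repeat replaces the visit |
|---|---|---|
| 26 | 27-31 (5) | 27-30 (4) |
| 27 | 28-31 (4) | 28, 29 (2) |
| 28 | 29-31 (3) | none |
| 29 | 30-31 (2) | none |
| 30 | 31-32 (2) | none |

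Total: 4 + 2 = 6 of 5 + 4 + 3 + 2 + 2 = 16 pairs. If a repeat takes at least 2 days to arrange (an assumption), the count is 4 of 11; at least 3 days, 2 of 6.

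**2. Unscheduled value from Day 19 to the day before Week 4.** The earlier value e is kept only if |e − 28| < |d − 28|. It is lost on 7 of 7 days (d = 26), 8 of 8 (d = 27), 9 of 9 (d = 28), 9 of 10 (d = 29) and 8 of 11 (d = 30).

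**3. Early termination up to Day 18 after a completed Week 1 visit on day w.** For measures taken at both visits, the early-termination value is kept only if |ET − 8| ≤ |w − 8|.

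- w = 8: all of Days 9-18 are dropped (10 of 10).
- w = 7, 8, 9: 9 + 10 + 9 = 28 dropped of 11 + 10 + 9 = 30.
- w = 6 to 10: 8 + 9 + 10 + 9 + 8 = 44 dropped of 12 + 11 + 10 + 9 + 8 = 50.
- Days 11-18 are always dropped. Early termination before any Week 1 visit is always kept.

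The measures concerned are vital signs, vIGA-AD, %BSA and EASI. Laboratory tests are drawn at early termination (Protocol 7.7) but not at Week 1 (Protocol 7.3). Selected per parameter, no early-termination laboratory value is lost; selected by whole visit, the same pairs as above are lost.

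**4. Size of one displacement.** 1/36 = 2.8%, 1/12 = 8.3%, 1/10 = 10%.

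**5. Effect of precedence.** If the scheduled visit always wins, step 1 falls from 6 of 16 to 0 of 16. Steps 2 and 3 are not cured by precedence alone, because there it is the unscheduled or early-termination value that is lost.

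**The case against.** The best counter-argument is textual. Section 7 keeps scheduled visits at their nominal label and applies the windows only to early-termination and unscheduled visits. On that reading the nearest-day rule might choose only among renumbered records and never displace a scheduled value. The wording does allow this. But once a repeat is renumbered to Week 4, the child has two Week 4 records, and the nearest-day rule is the only one offered for choosing between them. At best the SAP leaves the choice unstated.

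Several limits stand:

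- Replacement needs a visit on Day 26 or 27 and a prompt repeat. The planned repeat at Day 35 is a nominal Week 5 visit and does not compete.
- Repeats continue until normal or baseline, and Protocol 6.3.4 foresees values that do not normalise. A repeat after 1 to 4 days may still be abnormal, so the pull toward normal is a tendency.
- Clinically significant laboratory abnormalities are generally also adverse events (Protocol 8.1.1), and all data are listed.
- SAP 13.4 says by visit only for the quantitative summaries, not for the shift tables.
- The documents do not say whether repeats after Week 4 enter this database for children who roll over to the long-term study.

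A reader might go further and infer that most early-termination data are discarded and that the primary safety summaries as a whole are biased toward normal. The documents do not support that. Adverse events are not windowed, local tolerability is not scored at early termination, and early-termination laboratory values survive if selection is per parameter. For vital signs nothing shows that an early-termination reading should be more abnormal than the Week 1 reading, and SAP 13.5 separately tabulates markedly abnormal blood pressure changes and abnormal pulse values.

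**Conclusion.** The point holds for the laboratory shift and change tables. With a Week 4 visit on Day 26 or 27, the stated rule can replace a clinically significant abnormal value with a repeat that it prompted: 6 of 16 day pairs, none when the visit is on Day 28 or later. The error tends toward normal, and no worst-value summary offsets it. An adverse event record of the same abnormality does not correct the shift table, which reports a separately named primary endpoint.

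Two lesser consequences also hold. Unscheduled values from Day 19 up to Week 4 are usually displaced. After a Week 1 visit on Day 8, early-termination vital signs, vIGA-AD, %BSA and EASI on Days 9-18 leave the by-visit summaries; no direction of bias is shown for these.

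The conclusion assumes that a renumbered repeat competes with the scheduled record and that the repeat enters this study's database. The percentages per child show what one displacement would do; they are not an expected effect.

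**What to change.** In SAP Section 7, state that the scheduled visit takes precedence over unscheduled repeats in by-visit summaries and that selection is made per parameter. In SAP 13.4, add a laboratory shift table from baseline to the worst post-baseline value, using all scheduled, unscheduled and early-termination results. Add a last on-treatment row to the by-visit tables, defined so that early-termination assessments count.

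The cost is a few sentences of SAP text and minor extra programming. The shift tables may look slightly less favourable.

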8. ANALYSIS SETS

The safety population will include all enrolled subjects who receive at least 1 application of study drug. Subjects will be analyzed as treated. The safety population will be used for efficacy and safety analyses.

The PK population will include all subjects who undergo plasma PK sampling and have at least one evaluable concentration-time data available for analysis. A sample that is below the quantification limit (BQL) of the assay is considered evaluable. Subjects will be analyzed as treated.

The number of subjects screened, number enrolled, and the number of subjects in each population will be summarized.

9. STUDY POPULATION

9.1 Subject Disposition

Subject disposition information will be summarized and will include the number of subjects completing the treatment phase of the study, the number of subjects enrolling in the OL-LTE safety study, the number of subjects completing the study through follow-up and primary reason for discontinuation.

In order to describe the impact of COVID-19 on current study, the following disposition events will be summarized in the tables separately:

- Subjects discontinued from the treatment/study as a result of a positive COVID-19 diagnosis.
- Subjects discontinued from the treatment/study due to other reasons related to COVID-19. This is excluding COVID-19 diagnosis but may include reasons such as site closure, travel restrictions, fear of infection, etc.
- Subjects with study visits altered (including modified in-clinic visit, virtual and phone visits) and missed due to COVID-19.

COVID-19 related protocol deviations will be summarized separately. The impact of COVID-19 (including protocol deviation, visit alteration, treatment/study discontinuation and diagnosis of COVID-19) will also be flagged at subject-level in a data listing. Subject profile will be used to compile all COVID-19 related information for affected subjects.

Also, all COVID-19 related symptoms and confirmed cases that occur during the study will be reported as AEs and included in the summaries.

9.2 Protocol Deviations

Protocol deviations will be summarized by deviation category (major, minor). COVID-19 related protocol deviations will be summarized separately. Additionally, protocol deviations will be presented in a data listing.

9.3 Eligibility

Subjects not fulfilling any eligibility criteria will be presented in a data listing.

9.4 Demographic and Baseline Characteristics

Demographic variables include age, sex, ethnicity, race, and Fitzpatrick skin type. Age will be reported on the CRF and will be based on age at time of signing informed consent.

Other baseline characteristics include height, weight, body mass index (BMI), vIGA-ADTM, %BSA, EASI score, and PP-NRS.

Demographic and baseline characteristics will be summarized for the safety population. In addition, demographic and baseline characteristics will be listed by subject.

Medical history

The verbatim term of the medical history condition/event will be coded using the Medical Dictionary for Regulatory Activities (MedDRA), Version 24.0.

Medical history will be summarized in descending order based on subject count by system organ class (SOC) and preferred term (PT).

Atopic dermatitis history, cardiovascular risk factors, liver disease family history, previous COVID-19 diagnosis, and previous on-study COVID-19 vaccination will be summarized descriptively.

Medical history will be listed by subject.

9.5 Prior and Concomitant Medications

Prior and concomitant medication verbatim terms in the eCRFs will be mapped to Anatomical/Therapeutic/Chemical (ATC) class and preferred names using the WHODrug global dictionary (Version B3 01MAR2021).

Prior (within the 30 days before screening and with stop dates prior to date of first dose of study drug) and concomitant (ongoing or with stop dates on or after first dose of study drug) medications will be listed by subject. If the medication is ongoing or the stop year is missing, the medication will be considered as received for the entire duration of the study.

To distinguish prior vs concomitant medications, the following rules for stop dates will apply:

- If only year was recorded, and it is before Baseline year, it is a prior medication; if year is same or after Baseline year, it is assumed to be a concomitant medication.

- If day is missing, but month and year are before Baseline, it is a prior medication; if month and year are the same as Baseline, it is assumed to be a concomitant medication; if month and year are after Baseline, it is a concomitant medication.
- If start date is after Baseline, it is a concomitant medication regardless.

Prior and concomitant medications will be summarized separately by WHO ATC class and preferred name. These summaries will present the number and percentage of subjects using each medication. Subjects may have more than 1 medication per ATC class and preferred name. At each level of subject summarization, a subject is counted once if he/she reported 1 or more medications at that level. Each summary will be ordered by descending order of incidence of ATC class and preferred name within each ATC class.

Prior AD Medications

All systemic (oral and injectable) medications used by the subject for treatment of AD prior to 30 days before the Screening visit will be collected. Prior AD medications will be summarized by frequency count and percent by treatment and overall.

10. EFFICACY ANALYSES

All efficacy analyses will be performed based on the safety population.

10.1 Efficacy Variables

Efficacy endpoints include the following:

- Change in vIGA-AD™ score from Baseline at each study visit,
- Proportion of subjects who have a vIGA-AD™ score of clear or almost clear (0 or 1) and at least a 2-grade reduction from Baseline at each study visit,
- Proportion of subjects with $\geq 50\%$ improvement in EASI score from Baseline at each study visit,
- Proportion of subjects with $\geq 75\%$ improvement in EASI score from Baseline at each study visit,
- Proportion of subjects with $\geq 90\%$ improvement in EASI score from Baseline at each study visit,
- Mean change and percent change in EASI score from Baseline at each study visit,
- Mean change and percent change in %BSA affected from Baseline at each study visit,
- Mean change and percent change in %BSA x vIGA-AD™ from Baseline at each study visit
- Proportion of subjects with a Baseline PP-NRS score ≥ 4 who achieve ≥ 4 -point reduction in the average weekly PP-NRS from Baseline at each study visit,
- Proportion of subjects ≥ 12 years old with a Baseline PP-NRS score ≥ 4 who achieve a ≥ 4 -point reduction in the average weekly PP-NRS from Baseline at each study visit,

- Proportion of subjects 2 to <12 years old with a Baseline PP-NRS score ≥ 4 who achieve a ≥ 4 -point reduction in the average weekly PP-NRS from Baseline at each study visit,
- Mean change in average weekly PP-NRS score from Baseline at each study visit.

10.2 Baseline Values

Unless otherwise noted, baseline is defined as the last non-missing value recorded before the first dose of study drug. Unscheduled visits will be used in the determination of baseline values, when applicable.

10.3 Adjustments for Covariates

Not applicable.

10.4 Handling of Dropouts or Missing Data

Average weekly PP-NRS scores will be calculated for all nominal visits as the average of 7 daily post-baseline PP-NRS scores prior to and including the values assessed on the visit date. If daily PP-NRS scores are missing for more than 3 days in a 7-day period, the average weekly PP-NRS score will be set to missing.

Handling of partial or missing start and end dates for AEs can be found in Section 13.2.

No other missing data will be imputed.

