
 Incidence, frequency, and duration of treatment emergent adverse events (TEAEs) and serious adverse events (SAEs) Change from Baseline in laboratory values Change from baseline in vital signs Mean Investigator-assessed LTS scores by visit (overall and sensitive areas) Tapinarof plasma PK parameters on Day 1, if data permit, including: 
 area under the plasma concentration versus time curve from time zero to the last quantifiable concentration (AUC_{0-last}) maximum plasma concentration (C_{max}) time to maximum plasma concentration (t_{max}) time of last quantifiable concentration (t_{last}) Tapinarof plasma concentration on Day 28 	
Secondary:	

 Change in vIGA-AD™ score from Baseline at each study visit Proportion of subjects who have a vIGA-AD™ score of clear or almost clear (0 or 1) at each study visit Proportion of subjects with \geq50% improvement in EASI score from Baseline at each study visit Proportion of subjects with \geq75% improvement in EASI score from Baseline at each study visit Proportion of subjects with \geq90% improvement in EASI score from Baseline at each study visit Mean change and percent change in EASI score from Baseline at each study visit Mean change and percent change in %BSA affected from Baseline at each study visit Mean change and percent change in BSA x vIGA-AD™ values from Baseline at each study visit Proportion of subjects with a Baseline PP-NRS score \geq 4 who achieve \geq 4-point reduction in the PP NRS from Baseline at each study visit Proportion of subjects \geq 12 years old with a Baseline PP-NRS score \geq 4 who achieve a \geq 4-point reduction in PP-NRS score from Baseline at each study visit Proportion of subjects 2 to $<$ 12 years old with a Baseline PP-NRS score \geq 4 who achieve a \geq 4-point reduction in PP-NRS score from Baseline at each study visit Mean change in PP-NRS score from Baseline to Day 28 at each study visit by age group 	
Statistical Methods:	
Safety Analyses:	

 Analyses of the safety endpoints will be based upon the Safety population, which is defined as all enrolled subjects who receive at least 1 application of study drug. 	

- AEs will be summarized as incidence rates of any AEs, TEAEs, AEs of special interest, treatment-related TEAEs, TEAEs leading to study drug discontinuation, TEAEs leading to study discontinuation, and SAEs.

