- Changes in laboratory parameters and vital signs will be summarized using shift tables and descriptively for quantitative measures by visit.
- LTS scores will be summarized by visit.

Pharmacokinetics:

- Plasma concentration data will be listed and summarized by study visit. PK parameters will be presented in tabular and/or graphical format and summarized descriptively if data permit

Efficacy Analyses:

- Analyses of efficacy endpoints will be based upon the Safety population. Proportions will be summarized using frequency counts and percentages, and mean changes and percent changes will be summarized using descriptive statistics (mean, median, standard deviation, minimum and maximum).

Schedule of Assessments

Table 1: Schedule of Assessments

Procedures and Assessment	Screening	Treatment Phase					FU ^a	ET ^b
	V1	V2	V3	P/C	V4	V5	NA	
	Day -30 to Day -1	Baseline, Day 1	Day 8 (±1 day)	Day 15 (±2 days)	Day 28 (±2 days)	Day 35 (±3 days)	NA	
Informed consent	X							
Inclusion and exclusion criteria	X	X						
Demography	X							
Fitzpatrick skin type	X							
Brief physical exam ^c	X	X	X			X	X	X
Medical history ^d	X	X ^e						
Pregnancy test (females of child-bearing potential) ^f	X	X ^g				X		X
Blood sample for clinical laboratory assessments ^h	X					X	X ⁱ	X
Urinalysis	X					X	X ⁱ	X
Vital signs ^j	X	X	X			X	X	X
Study drug Dispensation / Collection ^k		D	C/D			C		C
Review instructions for study drug application ^l		X	X	X				
Dispense/collect subject diary of study drug application		D	C/D			C		C
Tapinarof cream administration in-clinic under site supervision ^m		X	X					
PK samples ⁿ	X	X				X		
AE/SAE review	X	X	X	X	X	X	X	X
Concomitant medication review	X	X	X	X	X	X	X	X
vIGA-AD TM score ^o	X	X	X			X	X	X
%BSA affected ^p	X	X	X			X	X	X
EASI ^p		X	X			X	X	X
LTS assessment by Investigator ^q		X	X			X		
PP-NRS (assessed pre-dose at visit, as applicable) ^r		X	X			X		
Enrollment (optional) in open-label long-term safety study						X		

- a. The Follow-up Visit will be performed for any subject who fails to qualify for participation in the open-label long-term safety study or qualifies to participate in the open-label long-term safety study but elects not to enroll in that study. A follow-up visit will be not completed for a subject who terminates early.
- b. Subjects who withdraw from the study before Day 28 (Visit 4) will complete an Early Termination Visit.

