6.2.3.1 Peak Pruritus Numeric Rating Scale

The PP NRS is a scale used to quickly assess itch/pruritus severity over a 24-hour period. The subject or caregiver will utilize the scale to assess peak pruritus QD and record the results in their daily diaries. The itch rating can be done before or after study drug administration since it should reflect the past 24 hours. On clinic visit days, the PP-NRS will be assessed in the clinic and not recorded in the diary. For subjects ages 2 to < 12 years, the PP-NRS will be completed by the parent or caregiver. For subjects ages \geq 12 years, the PP-NRS will be completed by the subject.

An example of the PP-NRS is provided below.

PP-NRS

On a scale of 0 to 10, with 0 being 'no itch' and 10 being 'worst itch imaginable', how would you rate your itch at the worst moment during the previous 24 hours?

PP-NRS © 2019 Regeneron Pharmaceuticals, Inc. and SAR&D. All rights reserved. Used with permission of Regeneron Pharmaceuticals, Inc. and SAR&D

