10.4 Planned Analyses

All safety, tolerability, PK, and efficacy measures over the course of the study will be presented. Details of planned analyses will be described in the Statistical Analysis Plan (SAP).

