10.4.4 Efficacy Analyses

All efficacy analyses will be based on the Safety population. The efficacy endpoints are as follows:

- Change in vIGA-AD™ score from Baseline at each study visit
- Proportion of subjects who have a vIGA-AD™ score of clear or almost clear (0 or 1) at each study visit
- Proportion of subjects with $\geq 50\%$ improvement in EASI score from Baseline at each study visit
- Proportion of subjects with $\geq 75\%$ improvement in EASI score from Baseline at each study visit
- Proportion of subjects with $\geq 90\%$ improvement in EASI score from Baseline at each study visit
- Mean change and percent change in EASI score from Baseline at each study visit
- Mean change and percent change in %BSA affected from Baseline at each study visit
- Mean change and percent change in BSA x vIGA-AD™ values from Baseline at each study visit
- Proportion of subjects with a Baseline PP-NRS score ≥ 4 who achieve ≥ 4 -point reduction in the PP NRS from Baseline at each study visit
- Proportion of subjects ≥ 12 years old with a Baseline PP-NRS score ≥ 4 who achieve a ≥ 4 point reduction from Baseline at each study visit
- Proportion of subjects 2 to < 12 years old with a Baseline PP-NRS score ≥ 4 who achieve a ≥ 4 point reduction from Baseline at each study visit
- Mean change in PP-NRS score from Baseline at each study visit by age group

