14. CHANGES TO PROTOCOL-SPECIFIED ANALYSES

Not applicable. There are no changes to the protocol-specific analyses.

Dermavant Sciences, Inc.
DMVT-505-2104

Statistical Analysis Plan, v1.0
08SEP2022

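### SAP Section 14 declares no changes, yet all four itch endpoints move from the protocol's PP-NRS at each visit to a 7-day average, which shows less improvement while itch is still falling

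*SAP*

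**What the plan says.** Protocol Section 10.4.4 lists four PP-NRS endpoints. Three are the proportion with a 4-point or larger fall among subjects with baseline 4 or more (overall, age 12 and over, age 2 to under 12), worded for the overall version as "reduction in the PP NRS from Baseline at each study visit". The fourth is "Mean change in PP-NRS score from Baseline at each study visit by age group". The protocol mentions no weekly average.

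A visit score exists. Table 1 schedules a pre-dose PP-NRS at Baseline, Day 8 and Day 28, and Section 6.2.3.1 says: "On clinic visit days, the PP-NRS will be assessed in the clinic and not recorded in the diary". On the other days a daily score goes into the diary.

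SAP Sections 10.1 and 11.1 restate all four endpoints on the average weekly PP-NRS. SAP Section 10.4 computes that value "as the average of 7 daily post-baseline PP-NRS scores prior to and including the values assessed on the visit date" and sets it to missing when more than 3 of the 7 days are missing. SAP Section 10.2 keeps the baseline as the last single value before the first dose. SAP Section 14 reads: "Not applicable. There are no changes to the protocol-specific analyses".

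**The concern.** The SAP replaces the measured quantity in every itch endpoint, and the section where a reader looks for departures says there are none. The study report could then present the itch results as following the protocol although the protocol does not define the variable behind them.

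Three things change with the definition:

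- **The value.** A mean over the preceding week includes days when a falling itch score was still higher.
- **The comparison.** A 7-day mean is set against a one-day baseline.
- **Who is counted.** A subject with a clinic score but more than 3 missing days drops out. A subject without a visit-day score but with enough diary days stays in. SAP Section 11.1 leaves missing values out of the percentages, so the denominator can move too.

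The trial tests no hypothesis, so the descriptive tables are the efficacy result. Subject listings keep the individual scores visible, but they do not give the visit-score response rate or mean change.

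**Working it through.** The plan states no itch effect, SD or power, so there is no figure of its own to reproduce. The textual comparison above settles the discrepancy for all four endpoints. The rest estimates how much it could matter.

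**Inputs from the documents.** Visits on Days 8 and 28, so the averaging windows are Days 2–8 and 22–28; a single-value baseline; a 0–10 scale; response as a fall of at least 4 among subjects with baseline at least 4; about 36 subjects.

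**Inputs assumed.** True baseline mean 6.5, SD 1.8; mean Day 28 reduction D of 3 or 4, SD between subjects 2; day-to-day SD 1.3; scores clipped to 0–10; several shapes of itch course. Each run used 200,000 simulated subjects, with and without integer rounding.

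**Closed form, exponential course.** With improvement proportional to f(d) = 1 − exp(−(d−1)/T), the weekly mean divided by the visit-day value is:

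| T (days) | Week 1: mean f(2..8) / f(8) | Week 4: mean f(22..28) / f(28) |
|---|---|---|
| 2 | 0.811 | 1.000 |
| 4 | 0.707 | 0.998 |
| 8 | 0.642 | 0.982 |
| 14 | 0.612 | 0.957 |

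**Closed form, linear fall over 27 days.** On Day 28 the visit value is D × 27/27. The mean over Days 22–28 is D × 24/27. The gap is D × 3/27, which is 0.33 for D = 3 and 0.44 for D = 4, before scores are limited at 0.

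**Simulation, Week 1** (visit score vs weekly mean; ranges run from D = 3 to D = 4):

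| Course | Mean reduction, D = 3 | Mean reduction, D = 4 | Response, integer scores | Response, unrounded |
|---|---|---|---|---|
| T = 2 | 2.89 vs 2.39 | 3.74 vs 3.11 | 42–57% vs 22–34% | 35–50% vs 21–34% |
| T = 4 | 2.52 vs 1.83 | 3.28 vs 2.39 | 35–48% vs 11–18% | 28–41% vs 10–17% |
| T = 8 | 1.89 vs 1.26 | 2.47 vs 1.64 | 23–32% vs 4–6% | 17–25% vs 3–6% |
| T = 14 | 1.47 vs 0.95 | 1.92 vs 1.23 | 15–22% vs 2–3% | 10–15% vs about 2% |
| Flat from Day 2 | 2.97 vs 2.97 | 3.83 vs 3.83 | 44–59% vs 34–50% | 37–52% vs 34–51% |
| 25% of effect lost on visit day | 2.31 vs 2.87 | 3.01 vs 3.71 | 31–43% vs 32–48% | 24–35% vs 32–48% |

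For the four exponential rows the mean-change gap runs from 2.89 − 2.39 = 0.50 to 3.28 − 2.39 = 0.89 points. The unrounded response gap runs from about 9 points (T = 14, D = 3) to 23 points (T = 4, D = 4). That is roughly 3 to 8 of 36 subjects if all had baseline 4 or more; the model puts 87–91% there.

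**Simulation, Week 4.**

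| Course | Mean-change gap | Response gap, integer | Response gap, unrounded |
|---|---|---|---|
| Exponential, T = 2–14 | 0.00–0.13 | about 8–12 points | about 1–5 points |
| Linear over 27 days | 0.29–0.36 | about 16 points (44% vs 28%, 59% vs 43%) | about 9 points |

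Near a plateau most of the integer-score response gap is rounding: a whole-number score reaches a 4-point fall more easily than a fractional mean. Under a linear fall more than half of the gap remains without rounding.

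**These ranges are not bounds.** A linear fall from 8 to 4 by Day 8 gives a weekly mean of 5.71, so the change is −2.29 against −4.00 on the visit score.

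**Reversal for one subject.** Baseline 8, Days 2–7 at 3, Day 8 at 5: the visit change is −3 (non-responder). The weekly mean is (6 × 3 + 5)/7 = 3.29, a change of −4.71 (responder).

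**The case against.** The strongest defence is that the protocol allows this. It collects daily scores, gives no rule for deriving the visit value, and in Section 10.4 leaves analysis details to the SAP. A weekly mean is also less noisy than one day's rating. All of that stands, and the averaging itself is not an error. But permission to choose a definition does not make it true that nothing changed.

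The defence is also right that a Section 14 entry alone would cure the false statement. The added tables go further. They are worth having because the listings do not supply the summaries that the protocol words.

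Four stronger readings are tempting and do not hold:

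- **Week 4 is safe.** This needs itch to have levelled off by Days 22–28. The documents give no itch course, and Protocol Section 1.2 reports efficacy responses in the earlier AD study continuing through Week 12, which does not establish a plateau by Week 4.
- **The effect is equally likely either way.** While itch falls, the weekly mean shows less improvement. In a separate simulation with a baseline mean of 7, it showed the larger mean improvement in at most 0.2% of 36-subject trials with an exponential fall. Reversal needs a visit day worse than the days before it, or chance when itch is flat (95% range about ±0.35 points at 36 subjects).
- **The SAP also changed the timing of the mean-change endpoint.** The Synopsis has "Mean change in PP-NRS score from Baseline to Day 28 at each study visit by age group", Section 2 refers to Day 28 only, and Section 10.4.4 to each visit. The SAP follows Section 10.4.4. The inconsistency is the protocol's own.
- **The main conclusions are at risk.** They are not; see the verdict.

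**Conclusion.** The point holds as a matter of text: all four itch endpoints rest on a different variable from the one in Protocol Section 10.4.4, and SAP Section 14 is incorrect in saying nothing changed.

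The size cannot be known from the documents. If itch is still falling at Day 8 along the exponential courses assumed, the weekly version understates the visit-score improvement by about 0.5 to 0.9 points and the response rate by about 9 to 23 percentage points unrounded, more with integer scores. At Week 4 the mean-change difference is negligible near a plateau and about 0.3 to 0.4 points under a continuing linear fall; response is lower in both cases. If itch is flat, mean change is the same.

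The endpoints are secondary and descriptive. No test, sample size or primary safety or PK result depends on them. The change should be made, but the trial does not turn on it.

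**What to change.** Replace the SAP Section 14 text with an entry saying that the four PP-NRS endpoints are analysed on the 7-day average defined in Section 10.4, against a single-value baseline, with the reason and the missing-day rule.

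Tabulate the visit-score versions of the same endpoints, from the clinic scores at Baseline, Day 8 and Day 28, beside the weekly versions. Label each clearly and show its denominator.

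The cost is SAP wording and one extra set of tables; no new data are needed and the weekly average stays. The same entry may also list the 2-grade vIGA-AD wording in SAP Section 10.1 and the tapinarof sulfate analyte in SAP Section 12, but neither bears on the itch results. The differing timing of the mean-change endpoint is for the protocol to reconcile.
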